#### **4.6 Sensitivity Analyses**

Three sets of sensitivity analyses will be run to help account for the complexities of the COVID-19 pandemic and the CMHC context. In the first set, the analyses for Aims 1-3 will be conducted with (a) treatment completers, (b) patients who completed more than half the number of the suggested sessions (i.e., > 2 sessions for Adapted and > 4 sessions for Standard), and (c) patients who completed half or fewer of suggested sessions. In other words, these analyses will test the effectiveness of TranS-C at varying doses, which may be important considering evidence on “early responders” (95) and “real world” contexts where turnover and dropout can be high (96,97). In the second set of sensitivity analyses, we will assess whether any patients who did not complete post-treatment or 6FU had achieved meaningful clinical improvement by mid-treatment, using a reliable change index for the primary outcome of PROMIS-SD (98). For the sensitivity analyses, we will define these patients (i.e., did not complete post-treatment or 6FU but achieved clinically meaningful improvement) as completers, and we will use their mid-treatment assessment in place of a post-treatment assessment. Then, all pre- to post-treatment analyses for Aims 1-3 will be rerun. In the third set of sensitivity analyses, we will run the analyses for Aims 1-3 but only include post-treatment and 6FU assessments that were collected within 3 months of the target assessment date (e.g., a 6FU assessment that was completed nine months after treatment ended).

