#### ***3.6.3 Generation 2 Patients***

Patient assessments in the immediate TranS-C treatment conditions are completed at pre-treatment, mid-treatment, post-treatment, and six months after treatment (6FU). Patient assessments in the UC-DT condition are completed at pre-treatment and four or eight weeks after pre-treatment (i.e., post UC-DT), depending on whether their county has been randomized to Adapted or Standard TranS-C, respectively. After the post UC-DT assessment, patients start delayed treatment with TranS-C. They subsequently complete assessments at mid-treatment, post-treatment, and 6FU. Note that patients do not complete a

6FU assessment after the delayed portion of UC-DT. This was a compromise made with CMHC partners, so that patients would not need to wait 7-8 months to receive treatment. See Figure 2 for patient timeline.

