### 3.7 Allocation

CMHCs and patients are randomized through a computerized randomization sequence. We do not stratify during randomization at the CMHC level. When randomizing patients, we stratify for presence of psychosis or not (current), presence of substance use or not (current) and age ( $\geq 50$  or not), as there is evidence these variables can impact sleep or treatment outcome (47,75,76). Only the facilitators, assessors, and research team (i.e., not CMHCs, local trainers, providers, or patients) are privy to which CMHCs and patients are allocated to which TranS-C treatment condition (Adapted versus Standard TranS-C). CMHC providers, local trainers, and patients know whether their patients have been randomized to receive the immediate or delayed treatment. The facilitator informs the local trainer once a patient can start having sessions, who then informs the provider. In the immediate condition, the provider is asked to begin sessions as soon as possible. In the delayed condition, the provider is asked to wait until after the patient has completed the post-delay assessment (i.e., approximately four weeks in the Adapted condition or eight weeks in the Standard condition).

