### 3.8 Sample Size

In the conceptualization of this study, the sample size goals for the Implementation Phase and the TTT phase combined were 96 providers and 576 patients (including 20% for attrition). During the conduct of the Implementation Phase of the study, we realized the immense value to knowledge of both the Implementation Phase and the TTT phase separately. Thus, we re-conceptualized the two phases as separate contributions. The Implementation Phase sample size remained as originally derived to power the analyses (42). The sample size of the TTT was guided by real-world factors, particularly the timeframe and budget for the study as well as the number of Generation 1 providers who are interested in recruiting, training, and supervising other providers. Additionally, in some CMHCs, many providers participated in Generation 1, leaving fewer providers to participate in Generation 2.

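### The second sensitivity set fills missing Aim 1 scores only for patients who improved, and only in immediate TranS-C, so agreement with the primary result does not show robustness to dropout; the attendance subsets of the first set do not test dose

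*Combined protocol and SAP*

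**What the plan says.** All references are to the combined protocol and SAP.

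- **Section 4.6, second set (set 2).** A reliable change index on PROMIS-SD identifies patients who had improved by mid-treatment but lack a later assessment. The plan says "we will define these patients (i.e., did not complete post-treatment or 6FU but achieved clinically meaningful improvement) as completers". On the value that such a patient then contributes, it says "we will use their mid-treatment assessment in place of a post-treatment assessment". The scope is wide: "Then, all pre- to post-treatment analyses for Aims 1-3 will be rerun".
- **Section 4.6, first set (set 1).** Aims 1-3 are repeated in treatment completers, in patients with more than half the suggested sessions, and in those with half or fewer. The stated purpose is: "In other words, these analyses will test the effectiveness of TranS-C at varying doses".
- **Section 3.6.3.** Immediate TranS-C has a mid-treatment visit. For the control arm, "Patient assessments in the UC-DT condition are completed at pre-treatment and four or eight weeks after pre-treatment". The mid-treatment visit of that arm belongs to delayed treatment: "They subsequently complete assessments at mid-treatment, post-treatment, and 6FU".
- **Section 3.7.** "In the delayed condition, the provider is asked to wait until after the patient has completed the post-delay assessment".
- **Table 2.** PROMIS-SD is the only patient outcome marked at mid-treatment.
- **Section 4.3.** Aim 1 has four outcomes: sleep disturbance (PROMIS-SD), sleep-related impairment, functional impairment and psychiatric symptoms.
- **Section 4.1.** The primary models use maximum likelihood on all available data, assuming data missing at random.

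**The concern.** A sensitivity analysis for dropout should show whether the conclusion survives plausible reasons for missing data. Set 2 adds back only dropouts already known to have done well, and in Aim 1 only one arm can supply them. It looks at the case where early responders leave. It does not correct the opposite case, where early non-responders leave and the primary model overstates the benefit. A reader who sees set 2 agree with the primary result could take it as evidence against that overstatement, which it is not.

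Set 1 has a different weakness. Attendance is known only after randomisation, so a difference between its subsets mixes any effect of dose with whatever made patients stay or leave.

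**Working it through.** **1. Who can supply a substituted value in Aim 1.**

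| | Pre-treatment | Between | Aim 1 endpoint |
|---|---|---|---|
| Immediate TranS-C | yes | mid-treatment PROMIS-SD | post-treatment |
| UC-DT | yes | no visit | post-delay (4 or 8 weeks) |

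The UC-DT mid-treatment score comes after the endpoint, during delayed TranS-C. Section 4.6 does not exclude UC-DT patients by name, but such a score would be an on-treatment value in the control arm. Only immediate TranS-C can supply a valid value. The one-arm problem is specific to Aim 1: in Aim 3 both versions of TranS-C have the visit, although the selection of improvers remains.

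**2. Which outcomes change.** One of the four Aim 1 outcomes has a mid-treatment score. For the other three the rerun has nothing to insert.

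**3. Size under random dropout.** The documents give no result to reproduce here. They give 130 patients (section 3.8) and one attrition figure, "576 patients (including 20% for attrition", from the combined plan for two phases. Assumed: 65 per arm (the patient allocation ratio is not stated), 40% as a second dropout rate, a mid-treatment score for every dropout, pre-post correlation r of 0.38 or 0.60 (pre-mid r + 0.1, mid-post r + 0.2), reliability 0.85 or 0.90, natural improvement 0 or 0.5 SD, and half of all change reached by mid-treatment. This makes eight settings.

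With dropout p, share of dropouts reliably improved q, pre-mid correlation ρ and improvement still to come m (half the total change):

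- cut-off c = 1.96 × √(2(1 − reliability))
- q = P(Z > (c − m)/s), with s = √(2(1 − ρ))
- shift ≈ [pq/(1 − p + pq)] × (b·e − m)

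Here e is how far the mean improvement of the substituted patients exceeds the average, and b = (1 − ρ − rρ + r)/(2(1 − ρ)) is the part that the pre/post model would not have predicted.

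*Low end, no true effect* (r = 0.60, reliability 0.85, no natural improvement): c = 1.96 × √0.30 = 1.07; s = √0.60 = 0.775; q = P(Z > 1.39) = 0.083; e = 1.43; b = 0.48/0.60 = 0.80; b·e = 1.14. Shift at 20%: (0.0166/0.8166) × 1.14 = 0.023 SD. At 40%: (0.0332/0.6332) × 1.14 = 0.060 SD.

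*High end, no true effect* (r = 0.38, reliability 0.90, no natural improvement): c = 0.877; s = √1.04 = 1.020; q = P(Z > 0.86) = 0.195; e = 1.44; b = 0.7176/1.04 = 0.69; b·e = 0.995. Shift at 20%: (0.039/0.839) × 0.995 = 0.046 SD. At 40%: (0.078/0.678) × 0.995 = 0.11 SD.

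*True effect 0.94 SD* (r = 0.60, reliability 0.90, natural improvement 0.5 SD): m = 1.44/2 = 0.72; q = P(Z > 0.20) = 0.42; b·e = 0.80 × 0.721 = 0.577; b·e − m = −0.143. Shift at 20%: (0.084/0.884) × (−0.143) = −0.014 SD. The sign can reverse, because a mid-treatment score may fall short of the improvement still to come.

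Across the eight settings with no true effect, 1-3.5 patients are substituted at 20% and 2-7 at 40%.

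**4. Selective dropout.** The table gives the error in the Aim 1 estimate by simulation (pre/post likelihood model, compound symmetry, 250,000 per arm, same eight settings). Positive means toward TranS-C. In the selective rows, dropout in TranS-C depends on mid-treatment improvement (logistic slope ±0.7 per SD), and UC-DT dropout is random.

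| Who leaves | True effect | Likelihood model, 20% / 40% | Set 2, 20% / 40% |
|---|---|---|---|
| At random | 0 | about 0 / about 0 | +0.02 to +0.05 / +0.06 to +0.11 |
| At random | 0.94 | about 0 / about 0 | −0.01 to +0.03 / −0.03 to +0.06 |
| Early non-responders | 0 | +0.05 to +0.07 / +0.10 to +0.13 | +0.06 to +0.07 / +0.13 to +0.16 |
| Early non-responders | 0.94 | as above | +0.04 to +0.07 / +0.06 to +0.14 |
| Early responders | 0 | −0.07 to −0.05 / −0.13 to −0.10 | −0.01 to +0.04 / −0.01 to +0.09 |
| Early responders | 0.94 | as above | −0.06 to +0.01 / −0.11 to +0.01 |

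A simpler regression version of the same check agreed within about 0.03 SD. At 65 per arm with random dropout, standard errors are 0.17-0.21 SD (20%) and 0.19-0.24 SD (40%). Type I error rises by 0.2-0.5 points at 20%, against a Monte Carlo error of about ±0.3, and by 1.2-2.8 points at 40%.

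**5. Set 1.** UC-DT patients are due no TranS-C sessions before their Aim 1 endpoint, so they have no matching attendance subset. Aim 2 outcomes are provider ratings, and 130/60 ≈ 2.2 patients per provider means that one provider's patients can fall in different subsets. No size is claimed for set 1.

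**The case against.** Set 2 is only a sensitivity analysis. Section 4.6 ties these analyses to the pandemic and the CMHC setting and, under set 1, cites evidence on early responders. It does not claim general robustness to dropout, and set 2 usually reduces the error when early responders leave. That stands, as does the small size at 20% dropout; the larger figures need an assumed 40%.

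The proposed replacement is not always better. It is itself a missing-at-random analysis. If dropout depends on post-treatment response, it errs by about 0.04-0.08 SD at 20% and 0.10-0.16 SD at 40%, even when every dropout has a mid-treatment score. With responders leaving in that way and no true effect, set 2 was closer to the truth in eight of eight settings. If only half the dropouts have a score, the replacement's residual error when dropout depends on mid-treatment response is 0.02-0.03 SD at 20% and 0.03-0.05 SD at 40%. This limits what the fix can promise, but a rule that admits only favourable values from one arm is still not a balanced check.

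Section 4.1 adds variables related to dropout as predictors. This does not settle the point: a mid-treatment score is measured after randomisation and, in the Aim 1 window, exists in one arm only.

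A reader might also infer that set 2 cannot be run for three outcomes, or that set 1 cannot be programmed. Neither follows. The rerun would execute and substitute nothing, so it is uninformative rather than impossible. All UC-DT patients could enter each set 1 contrast, so the missing entry rules are a matter of clarification.

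**Conclusion.** The concern holds for the design of the sensitivity analyses. In Aim 1, set 2 substitutes values selected as favourable, from one arm. Its agreement with the primary result cannot rule out overstatement from early non-responders leaving: depending on the setting, it leaves part of that error or adds to it. For three of the four Aim 1 outcomes it adds no information. Set 1 does not support the statement that it tests effectiveness by dose.

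With random dropout and no true effect, the shift is about 0.02-0.05 SD toward TranS-C at 20% dropout and 0.06-0.11 SD at 40%. These figures depend on the assumed correlations, reliability, 65 per arm and a mid-treatment score for every dropout.

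Three stronger readings are not supported. The primary intent-to-treat analysis is not biased by this rule. Set 2 does not always favour TranS-C, since at a true effect of 0.94 SD the sign is not fixed. No material type I error inflation is shown at 20%, the only attrition figure in the documents.

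**What to change.** 1. **Set 2, method.** Drop the responder condition. Use every available mid-treatment PROMIS-SD score, improved or not, as its own time point and not relabelled as post-treatment. For Aim 1, fit the mid-treatment mean in the TranS-C arm only: five means for five observed cells. Alternatively, use the score as an auxiliary variable in multiple imputation. State that this removes bias only if dropouts have a mid-treatment score and dropout depends on nothing beyond the observed scores. Report how many dropouts have one; section 4.2 already counts those who leave before the first session, who may have none. To probe departures from missing at random, a delta-adjusted analysis is the option.
2. **Set 2, scope.** Limit its patient outcomes to PROMIS-SD. State that an observed post-treatment score is never replaced, because the wording also covers patients who missed only 6FU. Do not use UC-DT scores from delayed TranS-C for the Aim 1 endpoint.
3. **Early responders.** Keep improvement among dropouts as the descriptive result already planned in section 4.2.
4. **Set 1.** Report the contrasts as descriptive for all aims and delete the sentence on varying doses. As a clarification, say how UC-DT patients enter Aim 1 and how providers are classed for Aim 2.

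The cost is SAP wording and modest programming, with no new data. The sensitivity estimate may be less favourable or less precise, and the gain is small where few dropouts have a mid-treatment score.

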#### **4.7 Exploratory Aim 1: Generation 1 Compared to Generation 2 on Patient Outcomes**

To compare Generation 1 and Generation 2 on primary and secondary patient outcomes of TranS-C, data from the Implementation Phase (see Sarfan et al., 2023) and the TTT Phase and both TranS-C conditions (Adapted and Standard) will be combined. MLM will be used to evaluate interactions between generation (Generation 1 or Generation 2) and time. The level 1 equation will include dummy-coded time indicators as the predictors (0 = pre-treatment, 1 = post-treatment). The level 2 equation will include dummy-coded generation (0 = Generation 1, 1 = Generation 2) and treatment by time interaction terms as predictors, adjusting for county. A significant interaction indicates a moderating effect of generation and will be probed with planned contrasts (e.g., effects of generation on change from pre-treatment to post-treatment) and graphs.

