### **3.3 Recruitment**

#### ***3.3.1 Community Mental Health Centers***

Building the CMHC network that forms the basis for this study began in August 2013 with outreach by the Principal Investigator (AGH). Originally, eight counties—each generally consisting of three to 10 CMHC sites—agreed to participate in the Implementation Phase. At various stages of the study, we have continued to focus on recruiting new counties and new CMHC sites to maximize provider and patient sample size goals for the Implementation and Train-the-Trainer Phases. For instance, all counties who participated in the Implementation Phase were invited to participate in the Train-the-Trainer Phase. Most elected to continue participating in the Train-the-Trainer Phase, with the exception of one county. Thus, to account for the latter, another county (Lake County) was recruited for the Train-the-Trainer Phase. Sites in the following nine counties in California, United States are currently participating in the Train-the-Trainer Phase: Alameda, Contra Costa, Kings, Monterey, Placer, Santa Cruz, Solano, Santa Clara, and Lake. Note that sites in San Luis Obispo are also participating but are operating as part of Monterey County.

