## **4 PLANNED ANALYSES**

### **4.1 Preliminary Analyses and Missing Data**

All analyses below pertain to the TTT Phase and are limited to Generation 2 providers and Generation 2 patients, except Exploratory Aim 1. For the primary analyses, which use multilevel modeling (MLM) and structural equation modeling, analyses will use all available data (intent-to-treat) (84). Models will be estimated with maximum likelihood estimation, and missing data will be assumed to be missing at random (85). For exploratory analyses using linear regression, approaches to missing data will be based on the number of missing cases (e.g., listwise deletion versus multiple imputation) (86). If dropout is related to other variables, they will be included as predictors. Baseline between-group differences in demographic variables will be examined. These tests will not be used to select covariates in the primary intention-to-treat analysis (87–90). Instead, covariates will be carefully selected at the conclusion of the trial—given the variations due to COVID-19 and the CMHC context (see Discussion)—and the potential influences of baseline differences will be evaluated as moderators (approach to moderation described below). Analyses comparing TranS-C to UC-DT will evaluate change in outcomes from pre-treatment to post-treatment. Analyses comparing Adapted to Standard TranS-C will evaluate change in Generation 2 outcomes from pre-treatment to post-treatment and pre-treatment to 6FU (see Method and Discussion for more details).

Distributions will be evaluated to detect outliers, and we will ensure that the assumptions of planned analyses are met. Covariates will include the patient variables for which we stratified (i.e., age and presence of psychosis or substance use). For all statistical models, counties will be adjusted for as a factor

variable rather than a level of analysis due to the relatively small number of clusters. The average intraclass correlation on provider and patient level outcomes will be reported.

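### Exploratory Aim 1 adjusts for county only as an additive factor, so a different county mix in the two generations can be read as a generation effect

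*Combined protocol and SAP*

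**What the plan says.** Section 4.7 pools Implementation Phase and Train-the-Trainer data, and "both TranS-C conditions (Adapted and Standard) will be combined". The test is stated as "MLM will be used to evaluate interactions between generation (Generation 1 or Generation 2) and time". The level 2 equation holds generation "and treatment by time interaction terms as predictors, adjusting for county". The section does not say what treatment means in that phrase. The result is to be read as follows: "A significant interaction indicates a moderating effect of generation and will be probed with planned contrasts".

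Section 4.1 explains the county adjustment for all models: "counties will be adjusted for as a factor" variable, not as a level of analysis. No section names a county × time term.

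On which counties take part, section 3.3.1 says "Most elected to continue participating in the Train-the-Trainer Phase, with the exception of one county" and that "another county (Lake County) was recruited for the Train-the-Trainer Phase". Section 3.8 adds that "in some CMHCs, many providers participated in Generation 1, leaving fewer providers to participate in Generation 2". Section 2 says that sites keep their original assignment to Adapted or Standard TranS-C, so version is fixed by county. The sensitivity analyses in section 4.6 cover Aims 1–3 only.

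**The concern.** A reader who sees that the model adjusts for county will assume that differences in county mix between the generations have been dealt with. They have not. The adjustment acts on the level of the score, while the hypothesis is about change. If patients in some counties improve more than in others, and those counties carry different weight in the two generations, the difference goes straight into the generation × time coefficient.

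The analysis is exploratory, but it is the plan's direct test of the question raised in section 1: whether outcomes hold once training passes to local trainers. An apparent loss of effect in Generation 2, or a masked one, could reflect only which counties supplied the patients.

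**Working it through.** The plan gives no sample size, power or detectable effect for Exploratory Aim 1, so there is no figure to reproduce.

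**1. What the additive factor does.** For patient *i* in county *c*, with G = 1 for Generation 2 and t = 0 or 1:

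y = a(c) + β·t + γ·G + θ·G·t + u(i) + e

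Post minus pre gives β + θ·G + noise. Both a(c) and γ drop out. With complete data, the estimate of θ is the difference in mean change between all Generation 2 and all Generation 1 patients. (With missing post-treatment scores the cancellation is no longer exact.)

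If mean change differs by county by an amount d(c), the estimate is centered on θ + Σ [p2(c) − p1(c)]·d(c), where p1 and p2 are the county shares in each generation. The second term is zero if the shares are equal or if the d(c) are all equal.

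**2. Check on one data set.** Data were simulated with no generation effect, a deliberately large version shift (Adapted share 21.2% in Generation 1, 75.4% in Generation 2) and a version difference in change of −0.5. The expected spurious effect is (0.754 − 0.212) × (−0.5) = −0.271. Mixed models fitted by maximum likelihood gave these generation × time estimates:

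- no county term: −0.300 (p = 0.002)
- additive county factor: −0.300 (p = 0.002), the same to at least five decimals
- county × time added: −0.047 (p = 0.67)

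This shows the mechanism. It does not estimate what will happen in the trial.

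**3. Version part alone.** Bias = (shift in Adapted share) × (Adapted–Standard difference in change). For assumed shifts of 0.05–0.30 and differences of 0.2–0.5 SD, it runs from 0.05 × 0.2 = 0.01 SD to 0.30 × 0.5 = 0.15 SD.

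**4. False-positive rate.** From the documents: 130 Generation 2 patients, and a cluster-size coefficient of variation of 0.72 (section 3.8, Aim 1, used here for county sizes). Two-sided alpha of 0.05 is stated for Aims 1 and 2 and assumed here. Also assumed: 10 counties (8 in both generations, 1 in each alone), 5 per version; county sizes drawn separately for each generation; Generation 1 N of 200 or 396; no true generation effect; 2,000 runs. Units are SDs of change.

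| County SD | Version difference | Additive county (N = 200 / 396) | County × time (N = 200 / 396) |
|---|---|---|---|
| 0 | 0 | 5.3% / 4.8% | 5.0% / 5.8% |
| 0.2 | 0 | 9.2% / 9.6% | 4.6% / 5.3% |
| 0.3 | 0 | 13.8% / 17.0% | 4.4% / 4.4% |
| 0 | 0.3 | 8.9% / 8.0% | 5.4% / 5.1% |
| 0.2 | 0.3 | 12.0% / 13.0% | 5.2% / 4.6% |
| 0.3 | 0.3 | 15.8% / 20.4% | 4.8% / 5.4% |

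Simulation error near 5% is about √(0.05 × 0.95 / 2000) = 0.5 percentage points.

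If only the immediate arm enters, and patients are split equally (the patient allocation ratio is not stated), Generation 2 contributes 130 / 2 = 65. The rate is then about 5–10% as written and about 4–6% with county × time.

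**5. Precision.** Without heterogeneity, the SD of the estimate rises from 0.111 to 0.134 (ratio 1.21) with Generation 1 N of 200, and from 0.101 to 0.122 (ratio 1.21) with N of 396. The smaller-sample run put the increase at the standard error as low as 16%.

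**The case against.** The strongest reply is that section 4.7 does contain a treatment-by-time term. In section 4.4, treatment means Adapted versus Standard. If it means that in 4.7 too, version × time is already in the model and the version part of the concern disappears. This stands as a possible reading. Because the versions are described as combined and the interaction is read as generation, the phrase may equally be carried over from the other aims to stand for generation × time. Either way, the county part remains and the term needs defining.

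A reader might infer that the documents show a shift in version mix. They do not. There are no counts by version, Lake's version is not stated, and one county leaving while another joins could leave the balance unchanged. A reader might also infer that counties exhausted their providers. Section 3.8 speaks of some centers, and of providers rather than patients, and a county generally has three to ten sites. The exact overlap is unknown as well: section 3.3.1 starts from eight counties, loses one and adds Lake, yet lists nine, and mentions continued county recruitment.

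The within-county contrast also answers a somewhat different question and costs precision in a trial that already expects to be underpowered. A ratio of 1.21 in standard error is 1.21² ≈ 1.46 in variance. That is fair, and is why the pooled contrast should be kept alongside. Sections 4.1 and 5 leave covariate choice to the end of the trial, but commit to no county or version interaction here.

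**Conclusion.** The point holds in conditional form. The stated county adjustment does nothing for the tested contrast, the county sets of the two phases differ, and the plan would read a resulting interaction as an effect of generation.

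It would go too far to say that the county mix will bias the result. If change is the same across counties and versions, there is no bias and the false-positive rate stays near 5%. Otherwise the rate is about 5–10% with 65 Generation 2 TranS-C patients and up to about 20% with the larger assumed samples. These figures rest on assumed county SDs of change of 0.1–0.3, a version difference of 0–0.3 SD, and county shares drawn independently for each generation. That last assumption tends to enlarge the difference in mix. In the trial itself the bias would be one fixed offset whose sign and size cannot be known from the documents.

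Because the comparison is exploratory and not randomized, this is an inexpensive improvement and does not threaten a primary conclusion.

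**What to change.** In section 4.7:

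- Say what the treatment-by-time term is: generation × time, or Adapted versus Standard × time.
- Add county × time, so that the generation contrast is made within county. This also absorbs version × time, because version is fixed by county. Show the pooled contrast next to it.
- State that counties present in only one generation do not inform the within-county contrast.
- Tabulate patients by county, version and generation.

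No new data are needed. The cost is a change of wording, about 9 degrees of freedom (10 assumed counties minus 1), and a standard error roughly 15–21% larger for the within-county contrast.
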